2.4 Secondary Endpoint(s)

The secondary endpoints are:

- The change from baseline in cognitive, functional, and global assessments by the end of study, including:
 - Alzheimer's Disease Assessment Scale-Cognitive Subscale (ADAS-Cog)
 - Mini-Mental State Exam (MMSE)
 - Alzheimer's Disease Cooperative Study-Activities of Daily Living (ADCS-ADL)

- Clinical Dementia Rating-Sum of Boxes (CDR-SB)
- Neuropsychiatric Inventory (NPI)
- The change from baseline in amyloid deposition by the end of study, including:
 - Mean standard uptake value ratio (SUVR), a composite summary of selected brain regions by the end of study
 - Whole brain amyloid burden (positive or negative) determined by visual assessment

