 - The MMSE is a 30-point questionnaire that is used extensively in clinical and research settings to measure cognitive impairment and is commonly used in medicine and allied health to screen for dementia. It is also used to estimate the severity and progression of cognitive impairment and to follow the course of cognitive changes in an individual over time; thus making it an effective way to document a participant’s response to treatment. The total score range is 0 – 30 and lower scores indicating greater impairment.
- Function: ADCS-ADL score is range of 0-78 and lower scores indicating greater impairment
- Global: CDR-SB

- The CDR-SB includes six domains (0-3 points/domain), with a total scoring range of 0 – 18 and higher scores indicating greater impairment. The CDR score is calculated at baseline for eligibility check.
- Behavior: NPI:
 - The NPI has 12 domains and for each domain, the relatives assess the frequency of the behaviour (4-point scale), the severity of the symptom (3-point scale) and the emotional stress for the caregiver (6-point scale). The total score of NPI is 0-144 and lower scores indicates greater impairment.

ADAS-Cog, ADCS-ADL, and NPI are rated at baseline (V1), Week 28 (V6), Week 52 (V10) and Week 78 (V13), while MMSE and CDR/CDR-SB are assessed at the first screening (S1), Week 24 (V5), Week 48 (V9) and Week 78 (V13). If a patient withdraws from the study prematurely during the study period or does not have any or some of the scores, the data will be treated as missing values, and no procedure for handling missing assessments will be applied.

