5.10 Analysis of Efficacy Data

Efficacy analyses will be performed on the mITT and PP populations. For change from baseline of ADAS-Cog total score, MMSE total score, ADCS-ADL total score, CDR-SB total score, NPI total score, A repeated-measures mixed-effects model with treatment (Arm 1 + Arm 2 vs. Arm 3, Arm 1 vs. Arm 3 and , Arm 2 vs. Arm 3), study visit, time-by-treatment, APOE4 status, and baseline as a covariate will be used to analyze change from baseline. The least square means using maximum likelihood estimate and its 95% will be provided. The unstructured covariance will be used in the modeling of the within-patient errors in the analysis.

For change from baseline of mean SUVR, A repeated- measures mixed-effects model with treatment (Arm 1 + Arm 2 vs. Arm 3, Arm 1 vs. Arm 3 and, Arm 2 vs. Arm 3), study visit, time-by-treatment, APOE4 status, and baseline as a covariate will be used to analyze change from baseline. The unstructured covariance will be used in the modeling of the within-patient errors in the analysis.

For change from baseline of mean SUVR by region, A repeated- measures mixed-effects model with treatment (Arm 1 + Arm 2 vs. Arm 3, Arm 1 vs. Arm 3 and, Arm 2 vs. Arm 3), study visit, time-by-treatment, and baseline as a covariate will be used to analyze change from baseline. The unstructured covariance will be used in the modeling of the within-patient errors in the analysis.

The p-values and confidence intervals for these efficacy endpoints were not adjusted for multiplicity, it should be used for screening purposes only, and that one side of 95% confidence intervals are provided to help gauge the precision of the estimates for treatment difference.

The proportion of PET positive subjects with visual read will be provided by number and percentage for each treatment group in mITT Population and PP Population at each post treatment scheduled visit. Treatment differences will be analysed with the Chisq test. The one-sided 95% confidence interval (CI, right side) between (Arm 1 + Arm 2 vs. Arm 3, Arm 1 vs. Arm 3 and, Arm 2 vs. Arm 3) from all visits will be calculated.

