Overall change from baseline for ARWMC frequency by visit will be summarized for safety population by treatment with number and percent of patients.

Visit value and Change from baseline for ARWMC will be summarized for safety population by treatment with n, mean, std dev, CV, Q1, median, Q3, Min, Max, L95 and U95.

Overall change from baseline for post- vaccine meningoencephalitis frequency by visit will be summarized for safety population by treatment with number and percent of patients.

5.13 **Sample Size**

This early phase clinical trial is exploratory in nature; hence, the sample size is determined to assess the primary objective of safety, tolerability, and immunogenicity of UB-311. The total of 45 subjects is planned to be enrolled, 15 per arms. For each UB-311-treated arm, 15 subjects are thought to be sufficient to detect an adverse event with an incidence of 7%. Furthermore, 30 subjects receiving UB-311 are anticipated to be able to detect an adverse event with an incidence of 4%.

With the current sample sizes, there may be limited power to detect a reduction in mean SUVRs or regional SUVRs unless there is a dramatic clearance of pre-existing plaques, and extremely limited power to detect effects on cognitive and functional endpoints. These analyses are therefore considered exploratory.

5.14 **Interim Analysis**

There is no interim analysis for this study.

5.15 **Multiplicity**

There is only primary immunogenicity endpoint in this study, and all efficacy endpoint will be served as secondary endpoint, and p-Value and its confidence interval will be used for screening purpose, so there is no multiplicity adjustment performed.

5.16 **General Conventions for Tables, Listings and Figures**

For summary tables, unless otherwise specified, the number of decimal places provided in the SAS output will be based on the accuracy of the least accurate value in the raw data as follows:

- n integer
- Arithmetic mean 1 decimal place more than the least accurate number in the raw data
- SD 2 decimal place more than the least accurate number in the raw data
- CV(%) 2 decimal places
- Geometric mean 1 decimal place more than the least accurate number in the raw data
- Median 1 decimal place more than the least accurate number in the raw data
- Minimum same number of decimal places as raw data

- Maximum same number of decimal places as raw data
- Confidence interval same number of decimals as the associated statistic

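### SAP 4.3 gives the NPI direction the wrong way round: a 0–144 total built from symptom ratings is said to mean more impairment when it is low

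*SAP*

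**What the plan says.** SAP 4.3 (Efficacy Variables) describes the five rating scales one by one and gives a range and a direction for each. The NPI entry gives 12 domains and says that, for each, "the relatives assess the frequency of the behaviour (4-point scale), the severity of the symptom (3-point scale"), together with a 6-point rating of the caregiver's emotional stress. It then states: "The total score of NPI is 0-144 and lower scores indicates greater impairment".

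The CDR-SB entry just before it, also a sum of points per domain, is given the opposite direction: "higher scores indicating greater impairment". ADAS-Cog is likewise described as higher = worse, and MMSE and ADCS-ADL as lower = worse.

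The NPI is a named secondary endpoint in Protocol 3.2.2 and SAP 2.4. SAP 5.10 analyses its total as change from baseline in the same repeated-measures model as the other scales: "For change from baseline of ADAS-Cog total score, MMSE total score, ADCS-ADL total score, CDR-SB total score, NPI total score". Protocol 6.3.1 lists the NPI under behaviour without a direction. The SAP 4.3 sentence is the only statement of direction in either document.

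**The concern.** Frequency, severity and stress are measures of burden. A total built from them should rise as behaviour worsens, so the sentence contradicts the description directly before it.

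The direction statement tells a reader whether a change from baseline is a gain or a loss. The five scales do not all run the same way, so the reader depends on it. The introduction to the SAP says that it sets the rules for determining endpoint outcomes and that its analyses are meant for regulatory submission and manuscripts. A programmer who labels outputs from SAP 4.3, or an author who writes the results from it, would report an NPI benefit as harm and a harm as benefit.

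**Working it through.** **Inputs, all from SAP 4.3:** 12 domains; frequency on 4 points; severity on 3 points; caregiver stress on 6 points; total 0–144; stated direction lower = worse.

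**Assumptions.** The SAP prints no scoring rule and no item anchors. I assume that more points mean more frequent, more severe or more stressful, and that a domain without symptoms scores 0 where ratings otherwise start at 1.

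**Step 1: reproduce the stated range.** Candidate rules, summed over 12 domains:

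| Rule per domain | Total range | Gives 0–144? |
|---|---|---|
| frequency (1–4) × severity (1–3), absent = 0 | 0 to 12 × 4 × 3 = 144 | yes |
| frequency + severity + stress (0–5), absent = 0 | 0 to 12 × (4 + 3 + 5) = 144 | yes |
| frequency × severity, no code for absent | 12 to 144 | no |
| frequency (0–3) × severity (0–2) | 0 to 12 × 6 = 72 | no |
| frequency + severity, absent = 0 | 0 to 12 × 7 = 84 | no |
| frequency (0–3) + severity (0–2) | 0 to 12 × 5 = 60 | no |
| frequency + severity + stress (1–6), absent = 0 | 0 to 12 × 13 = 156 | no |
| frequency (0–3) + severity (0–2) + stress (0–5) | 0 to 12 × 10 = 120 | no |
| frequency × severity + stress (0–5), absent = 0 | 0 to 12 × 17 = 204 | no |
| frequency × severity × stress (1–6), absent = 0 | 0 to 12 × 72 = 864 | no |
| stress alone (0–5) | 0 to 12 × 5 = 60 | no |

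Two rules reproduce the SAP's range exactly.

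**Step 2: direction under those two rules.** Each extra point of frequency or severity raises the domain score, and under the second rule so does each extra point of stress. In both, 0 is a subject with no symptoms in any domain and 144 is a subject at the maximum in all 12. Higher is worse.

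**Step 3: could reverse coding rescue the sentence?** Suppose the items ran the other way, with 1 the most frequent and most severe. For the product, all 12 domains present at their worst would total 12 × 1 × 1 = 12. For the sum, with 0 the greatest stress, the total would be 12 × (1 + 1 + 0) = 24. Neither reaches 0. A total of 0 would still need every domain to be absent, so the lowest score would still belong to the symptom-free subject.

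**Step 4: the five directions side by side.** As written, lower = worse for MMSE, ADCS-ADL and NPI (3) and higher = worse for ADAS-Cog and CDR-SB (2). With the NPI corrected, lower = worse for 2 and higher = worse for 3.

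**Step 5: what changes numerically.** SAP 5.10 models the change in NPI total whatever the direction is called. SAP 5.1 makes tests two-sided at 0.05 unless otherwise specified. Estimates and two-sided p-values are therefore the same before and after the correction.

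**The case against.** The strongest reply is that this is a slip in a descriptive bullet. The direction enters no derivation: the SAP defines no NPI responder, no improved or worsened category for the rating scales, and no composite across them. SAP 5.10 says of the unadjusted efficacy p-values and intervals that "it should be used for screening purposes only", and SAP 5.13 says of the SUVR, cognitive and functional endpoints: "These analyses are therefore considered exploratory". A careful reader would notice the conflict with the component description, and Protocol 6.3.2.1 requires trained raters, so data collection is not in doubt. All of this stands, and it limits the weight of the point.

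A second objection is that the scoring rule is inferred. This also stands in part. Matching 144 does not identify the rule, because one fitting rule counts caregiver stress and the other does not. It does not rescue the sentence, because both rules run the same way and reverse coding fails at the lower end.

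One point cuts the other way. SAP 5.10 also offers one-sided 95% limits for treatment differences and does not say which side is used for the scales. If the side were chosen by the direction of benefit, the wrong NPI direction could put or read the limit on the wrong side. The SAP does not tie the two together, so this is a possibility only.

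**Conclusion.** The concern holds. The NPI direction in SAP 4.3 contradicts the components and range given in the same bullet, and no other passage corrects it. It affects one of five secondary rating scales, whose whole 0–144 range is read in reverse.

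The consequence is misinterpretation of NPI results: no model estimate, two-sided p-value, sample size or data item changes. It should be corrected because the sentence is the plan's only instruction on how to read a named secondary endpoint, but it does not threaten the trial's primary conclusions.

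The conclusion rests on the ordinary reading of frequency and severity ratings (more points, more symptoms) and on 0 meaning no symptoms. It does not depend on which of the two fitting rules the sponsor uses.

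**What to change.** In the NPI entry of SAP 4.3, replace 'lower' with 'higher', so that higher totals indicate greater impairment. Make any NPI output labels, footnotes and report text that state a direction follow.

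In the same edit it would help to add one sentence saying how the total is formed and whether caregiver stress is counted, because both frequency × severity and frequency + severity + stress (0–5) give 144 and they are different variables.

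The cost is one corrected sentence and one optional added sentence. Data collection, models, tests and sample size are untouched.

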4.3.1 SUVR Composite

Mean SUVR change from baseline will be evaluated for a composite target region comprised of a weighted average of selected regions of interests such as frontal, temporal, parietal, occipital and precuneus. The corresponding reference region will be the whole cerebellum for the secondary endpoint. The SUVR is computed as the ratio of the target region signal to the reference region signal.

4.3.2 Semi-Quantitative Visual Assessment

The semi-quantitative visual assessment method will be used to visually assess amyloid burden. The change from baseline in the proportion of PET positive subjects with visual read will be evaluated.

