### 4.2 Inclusion Criteria

For inclusion in the study subjects must fulfil all of the following criteria:

1. Male or female aged between 60-90 years old.
2. Probable Alzheimer's disease based on the National Institute of Neurological and Communicative Disorders and Stroke and the Alzheimer's Disease and Related Disorders Association (NINCDS-ADRDA) criteria and National Institute on Aging-Alzheimer's Association (NIA-AA) guidelines.
3. Mini-Mental State Examination (MMSE) scores between 20 and 26 (inclusive).
4. Clinical dementia rating (CDR) scores of 0.5 or 1.
5. At least 6 years of education or sufficient work history (to exclude mental retardation).
6. Visual and auditory acuity adequate for neuropsychological testing.
7. Stable doses of permitted medications for 3 months before screening, such as acetyl cholinesterase (AChE) inhibitors, N-methyl-D-aspartate (NMDA) receptor antagonist, ergot alkaloids or their derivatives for cognitive enhancement.
8. Hachinski ischemic score (HIS)  $\leq 4$  (original score).
9. Geriatric Depression Scale-Short Form (GDS-SF)  $< 6$ .
10. Eastern Cooperative Oncology Group (ECOG) performance status 0-2.
11. Female must either be post-menopausal (no menstrual period for  $> 1$  year), surgically sterilized or agree to avoid becoming pregnant during the entire period of this study; while sexually active fertile male must agree to use effective birth control methods throughout the study duration, if their sexual partner(s) are women of childbearing potential.
12. With a caregiver who has frequent contact with the subject (e.g. an average of 10 hours per week or more) and agrees to sign the informed consent form (ICF), to perform study-related AD scales and to accompany or delegate a companion with the subject to all visits. A companion needs not to be a family member (with kinship).
13. Both patient and his/her caregiver should sign the written informed consent before undergoing any study procedures.
14. Agree not to donate blood or blood products for transfusion during the study and for 3 months thereafter.

15. A positive of A $\beta$  plaque on 18F-AV-45 PET by an imaging expert (confirmed during the second stage of screening per central independent review).

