#### 3.3 PET Central Independent Review

For the PET eligibility review, sites are required to submit screening 18F-AV-45 PET scans acquired during the second stage screening immediately to the Imaging Corelab to confirm the presence of amyloid deposition and study eligibility. An independent reviewer will confirm the presence of amyloid deposition on the PET scans by conducting a visually qualitative assessment and making a determination for Aβ+ (amyloid positive) or Aβ- (amyloid negative). The Independent Reviewer will make the determination of Aβ+ (amyloid positive) or Aβ- (amyloid negative) based on a standard uptake value ratio (SUVR) threshold cutoff value (qAb-).

Semi-quantitative visual rating 18F-AV-45 PET images will be conducted for each enrolled subject and all available visits: the Independent Reviewer (qualified nuclear medicine physician) will rate

each PET image independently for amyloid burden based on successive levels of 18F-AV-45 retention.

A quantitative analysis of PET image data will be performed utilizing PET software such as MIMNeuro for enrolled subjects and respective visits. The 18F-AV-45 PET images will be fitted to region overlays to quantify the mean cortical to cerebellum SUVR calculated from cortical regions, such as frontal cortex, temporal cortex, precuneus, parietal cortex, anterior cingulate, and posterior cingulate, relative to the whole cerebellum reference region.

18F-AV-45 PET follow up visits will be acquired at week 52 and week 78 to assess the changes in A $\beta$  burden from the baseline. Semi-quantitative and quantitative analysis will be performed as described above.

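### The visual PET endpoint in the SAP is by design only a rate of conversion to amyloid-negative, and the graded visual rating made on every enrolled subject's scans has no planned analysis

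*SAP*

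**What the plan says.** - **Endpoint.** SAP 2.4 lists among the secondary endpoints "Whole brain amyloid burden (positive or negative) determined by visual assessment". Protocol 3.2.2 lists only SUVR for amyloid burden, so the visual endpoint is an addition made in the SAP.
- **Variable.** SAP 4.3.2 is headed as a semi-quantitative visual assessment and says that method will be used. The variable it then defines is binary: "The change from baseline in the proportion of PET positive subjects with visual read will be evaluated".
- **Analysis.** SAP 5.10: "The proportion of PET positive subjects with visual read will be provided by number and percentage for each treatment group". This is done at each post-treatment visit, and arms are compared by chi-square. SAP 5.1 sets two-sided tests at 0.05.
- **Entry.** Protocol 4.2, criterion 15, requires a positive scan for "plaque on 18F-AV-45 PET by an imaging expert (confirmed during the second stage of screening per central independent review").
- **Baseline.** SAP 4.1 takes the last value before the first injection. Protocol 6.3.2.2 schedules PET at S2, Week 52 and Week 78, so S2 is the only scheduled pre-dose scan.
- **Graded rating.** Protocol Appendix 1, section 3.3, has the independent reviewer rate "each PET image independently for amyloid burden based on successive levels of 18F-AV-45 retention". This is done for each enrolled subject at all available visits. The number and definition of the levels are not given.

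**The concern.** The same scan serves as the entry criterion and as the baseline of the endpoint. A subject whose visual rating falls by one or more levels but stays positive contributes nothing to the endpoint. The plan collects a finer visual measure on the same scans and specifies no analysis for it. What is at stake is the information from one secondary endpoint. The chosen test is also fragile here: it has small expected counts where it first reaches significance, and no result if every scan stays positive.

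**Working it through.** The documents give no power, sample size or expected rate for the visual endpoint, so there is no stated figure to reproduce.

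**Step 1: what the variable reduces to.** With a baseline proportion of 1 in each arm, change = (proportion positive at visit) − 1 = −(converted to negative)/n. Only conversions enter.

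**Step 2: conversions needed.** Inputs are 15 per arm (SAP 5.13) and two-sided alpha 0.05. I assume that all subjects have an evaluable scan and that 0/15 convert on placebo. For *a* conversions among n₁ active and 0 among n₂ = 15 placebo subjects, with N = n₁ + n₂:

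χ² = N(a·n₂)² / [n₁·n₂·a·(N − a)]

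For 4/15 v 0/15: χ² = 30 × 60² / (15 × 15 × 4 × 26) = 108,000 / 23,400 = 4.62, p = 0.032.

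For 7/30 v 0/15: χ² = 45 × 105² / (30 × 15 × 7 × 38) = 496,125 / 119,700 = 4.14, p = 0.042.

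| Active v 0/15 | Chi-square p | Fisher p | Smallest expected count |
|---|---|---|---|
| 3/15 | 0.068 | 0.22 | 1.5 |
| 4/15 | 0.032 | 0.10 | 2.0 |
| 5/15 | 0.014 | 0.042 | 2.5 |
| 6/30 | 0.063 | 0.16 | 2.0 |
| 7/30 | 0.042 | 0.077 | 2.3 |
| 8/30 | 0.027 | 0.038 | 2.7 |

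The smallest expected count is 15a/N. At the chi-square threshold it is 2.0 or 2.3, and the exact test does not agree that the result is significant.

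**Step 3: no conversions.** If a = 0 in both groups, the expected counts in the negative column are zero and the statistic is 0/0. The SAP names no fallback test.

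**Step 4: power.** With no placebo conversions, power is P(X ≥ 4) for X ~ Bin(15, q), or P(X ≥ 7) for X ~ Bin(30, q). The rows with 5% of placebo subjects read negative come from summing over all pairs of outcomes.

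| True conversion on UB-311 | 10% | 20% | 30% | 40% |
|---|---|---|---|---|
| 15 v 15, placebo 0% | 6% | 35% | 70% | 91% |
| 30 v 15, placebo 0% | 3% | 39% | 84% | 98% |
| 15 v 15, placebo 5% | 3% | 19% | 45% | 70% |
| 30 v 15, placebo 5% | 1% | 21% | 55% | 82% |

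**Step 5: graded against binary (illustration only).** Every input is assumed, because the documents give no scale and no rates: levels 0 to 4, positive at 2 or more, a fall in 40% on UB-311 and 10% on placebo, 30 v 15, and 6,000 simulated trials per row. The rank test is a Wilcoxon rank-sum test on change in level.

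| Baseline levels 2/3/4 | Size of fall | Binary chi-square | Rank test |
|---|---|---|---|
| 15/35/50% | one level | 1% | 57% |
| 15/35/50% | two levels | 20% | 57% |
| 50/30/20% | one level | 20% | 56% |
| 50/30/20% | two levels | 47% | 57% |

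The rank test has the higher power in each row. The margin runs from about 10 to 56 percentage points, so its size depends on the assumptions.

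**The case against.** Several parts of the case for the plan stand.

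- **SUVR already measures partial clearance.** A reader might infer that the trial cannot answer its secondary objective on amyloid deposition. The documents do not support that. Composite SUVR is a secondary endpoint, regional SUVR is exploratory (SAP 4.3.1 and 4.3.3), and both are analysed by repeated-measures models in SAP 5.10. The loss is confined to the visual endpoint.
- **Conversion to negative is a legitimate question.** A reader might say the endpoint is stuck at a ceiling. It is not: it starts at one end of its range and is free to move in the direction of benefit, as any responder rate is.
- **A result of 100% v 100% cannot be predicted.** SAP 5.13 says power for SUVR is limited unless clearance is dramatic, but it gives no expected conversion rate. The protocol's introduction reports plaque removal after a different active amyloid vaccine. Conversion is uncertain, not excluded.
- **The 100% baseline is by design, not certain.** Appendix 1 section 3.3 describes the eligibility call as "conducting a visually qualitative assessment and making a determination for Aβ+ (amyloid positive) or Aβ- (amyloid negative"), and also as "based on a standard uptake value ratio (SUVR) threshold cutoff value". If the cutoff decided entry, or the S2 scan is re-read, the visual baseline could fall below 100%. That departure would reflect reader or method disagreement, not treatment, which is a reason to name the baseline read.
- **The levels might still be tabulated** under the general rule for categorical data in SAP 5.1. But no variable or table for them is specified, and no comparison between arms.
- **These analyses are for screening.** SAP 5.10 says so of the efficacy p-values, and SAP 5.13 calls the SUVR and clinical analyses exploratory. This limits the consequence. It is not a reason to leave collected graded data without an analysis.

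**Conclusion.** The point holds for the visual endpoint alone. As written, it is a conversion rate that scores any smaller visual reduction as no change, while a graded rating of the same scans has no planned analysis. With no placebo conversions, significance by chi-square needs 4/15 (27%) in one active arm or 7/30 (23%) pooled. Power is poor at 10% true conversion (about 6% for one arm, 3% pooled) and reasonable only from about 30% (70% and 84%). The test is unreliable at its threshold and undefined if nobody converts. These figures assume 15 evaluable scans per arm and a visual baseline of 100%. A graded analysis should be more sensitive to partial change, but by how much cannot be stated without the core lab's scale. Priority is low, since no primary conclusion is affected.

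**What to change.** 1. In SAP 2.4, 4.3.2 and 5.10, make the visual endpoint the change from baseline in the reviewer's semi-quantitative level at Weeks 52 and 78. Compare Arm 1 + Arm 2, Arm 1 and Arm 2 each with Arm 3 by a rank or proportional-odds method. State the levels and which of them count as positive.
2. State which S2 read is the baseline: the eligibility call or the semi-quantitative rating. If it is the eligibility call, say whether that is visual or by SUVR cutoff.
3. Keep conversion to negative as counts per arm with exact intervals. If a test is kept, use an exact test in place of chi-square.

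**Cost.** SAP wording and one changed analysis. No new scan or read is needed, because Appendix 1 section 3.3 already requires the rating. The downside is small: the gain depends on how fine the core lab's scale is, and a very coarse one would add little.
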